16.4 Procedures for reporting deviation(s) from the original SAP

These will be submitted as substantial amendments where applicable and recorded in subsequent versions of the protocol and SAP.

16.5 Termination of the trial

Progression criteria for the internal pilot phase are described in section 13. There is potential for the study to terminate early if our funder assesses the trial as not being feasible following an assessment of progress against our targets at the end of the internal pilot with input from our TSC and IDMC. There is also the possibility of terminating the trial early for either effectiveness or futility following the planned interim analysis, which will be detailed in the PRONTO IDMC charter and interim SAP.

17 Analysis

17.1 Main analysis

The primary analysis will be intention to treat and will fit separate two-level logistic regression models (patients nested within sites) to both primary outcomes (antibiotic initiation and mortality), controlling for baseline NEWS2 score (minimisation factor). The intervention will be considered effective if there is both a significant reduction in antibiotic initiation AND if the difference in mortality between the two group is negligible (i.e. non-inferior). (See section 5.3 for the primary outcome for effectiveness table which includes antibiotics and mortality outcomes.)

A planned interim analysis of the co-primary outcomes will be conducted when 50% of patients have been recruited and followed up for 28 days. Stopping the study shall be recommended by the IDMC based on group-sequential O'Brien-Fleming boundaries [37, 38]. They shall recommend stopping for effectiveness if:

- the PCT guided assessment is superior in terms of 28-day mortality (i.e. a significant reduction to less than 15%), or
- the PCT guided assessment is non-inferior in terms of 28-day mortality and superior in terms of initiation of antibiotics.

They shall recommend stopping for futility if the results of the interim analysis suggest futility for both endpoints.

In case the 28-day mortality rate in the control arm deviates from the assumed 15%, the absolute 2.5% non-inferiority margin will be replaced with an arcsine difference 'non-inferiority frontier' [39].

The final primary analysis will be adjusted to account for the interim analysis. Imputation of missing data will be done as part of sensitivity analyses.

In a secondary analysis, complier adjusted causal effect models will be fitted to allow for non-adherence to the intervention. Two models will be fitted allowing for two different definitions of adherence:

1. Patients randomised to PCT guided care in whom a PCT test is done and the clinician considers the results as part of their decision making.
2. Patients randomised to PCT guided care in whom a PCT test is done and the clinician follows the algorithm exactly.

All secondary analysis will also be performed based on intention to treat and utilising two level models to allow for patients nested within sites. The following analyses will be undertaken (Table 3):

Table 3: Planned outcomes and analyses

Outcome	Measure	Time frame	Analysis
Antibiotic initiation	Time until initiation	In ED	Cox regression
Antibiotic usage	No of days on IV antibiotics No of days on all antibiotics No of days on broad spectrum antibiotics	In hospital	Linear regression
Antibiotic adverse outcomes	Anticipated drug reactions include: diarrhoea, C. difficile , acute kidney injury, hearing loss etc.	In hospital	Logistic regression
ICU usage	People admitted to ICU No of days in ICU	In hospital	Logistic regression Linear regression
Readmission to hospital	People with one or more readmissions	After discharge	Logistic regression
Mortality	Time until death	90* days	Cox regression
Health utility	EQ-5D-5L	90* days	Linear regression of transformed outcome measure

* Except for patients recruited during the last 3 months of the study.
Full details of all analyses will be provided in the PRONTO SAP.

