In the busy environment of an ED or Acute Medical Unit (AMU), risk stratification currently relies on NICE sepsis guidelines and the National Early Warning Score (NEWS2) assessment based on six vital signs and requirement for supplemental oxygen [9]. The challenge of delivering high quality sepsis care in an ED setting has been well recognised [10, 11]. Accurate risk stratification could improve antimicrobial stewardship where clinical teams feel confident that they can safely assess and wait for results of initial investigations prior to commencing antibiotics within 3 hours, but not within the 1 hour target. The use of screening tools for sepsis within EDs in the UK remains a point for discussion. The third international consensus definition (Sepsis 3) recommended use of a new, rapid scoring tool, the quick Sequential Organ Failure Assessment (qSOFA) score, to identify patients at high risk of death and prolonged ICU stay [1]. A qSOFA ≥ 2 is used as an indicator of screening tool for sepsis. Current NHS England policy is for NEWS2 score to be adopted by all hospitals in England by April 2019 in order to facilitate detection of deterioration and sepsis [9]. NEWS2 has been demonstrated to have comparable diagnostic accuracy in detection of severe outcomes and is more widely used in the NHS than qSOFA [12, 13]. NHS England recommends that if a NEWS2 ≥ 5 is accompanied by suspicion of sepsis, this should prompt the senior clinical decision-maker,

using clinical judgment, to start appropriate treatment (intravenous antibiotics and fluids), as indicated, within an hour of the risk being recognised. A NEWS2 ≥ 5 rather than qSOFA ≥ 2 (which is more comparable to NEWS2 ≥ 7) as threshold for the screening for sepsis reduces specificity and increases the number of patients considered to be in a high risk group from approximately 20-25% to 50-75% [unpublished RLBUHT data]. Several further evaluations of alternative scoring systems including a retrospective cohort study from our hospital [12] have concluded that whilst differences in the scoring systems exist, no scoring system has both high sensitivity and specificity for predicting adverse outcomes in sepsis in the ED, and NEWS2 is more accurate than qSOFA for predicting adverse outcomes.

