8.1 Inclusion criteria

Patients \geq 16 years presenting to the ED with suspected sepsis.

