15.5 Reporting procedures

15.5.1 Participating Site Responsibilities

The PI (or delegated appropriately qualified doctor from the trial team) should sign and date the SAE CRF to acknowledge that he/she has performed the seriousness and causality assessments. Investigators should also report SAEs to their own health boards or trust in accordance with local practice.

A completed SAE form for all events requiring immediate reporting should be sent via email to the CTR within 24 hours of knowledge of the event. A separate form must be used to report each event, irrespective of whether or not the events had the same date of onset.

The participant will be identified only by trial number, date of birth and initials. The participant's name should not be used on any correspondence.

It is also required that sites respond to and clarify any queries raised on any reported SAEs and report any additional information as and when it becomes available through to the resolution of the event. Additionally, the CTR may request additional information relating to any SAEs and the site should provide as much information as is available to them in order to resolve these queries.

Serious Adverse Event (SAE) email address:

[contact]

Serious adverse events should be reported from randomisation, throughout the treatment period up to, and including 28 days after the participant is randomised.

An SAE form is not considered as complete unless the following details are provided:

- Full participant trial number
- An Adverse Event
- A completed assessment of the seriousness, and causality as performed by the PI (or another appropriately medically qualified doctor registered on the delegation log).

If any of these details are missing, the site will be contacted and the information must be provided by the site to the CTR within 24 hours.

All other AEs should be reported on the CRF following the CRF procedure described in Section 16.

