16.1 Randomisation

Individual patients with suspected sepsis will be randomised in a 1:1 ratio to either standard clinical management (control) or standard clinical management plus PCT guided assessment (intervention). We will use minimisation with NEWS2 score and site as stratification factors and a random element to reduce the risk of subversion [35]. This will be implemented in a secure 24-hour web-based randomisation programme controlled centrally by the Centre for Trials Research in Cardiff. Details of the randomisation procedure will be specified in a separate randomisation plan.

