16.2 Sample size

The sample size calculation is based on two co-primary outcomes [36] :

1. 28-day mortality, for which we want to show non-inferiority of the PCT guided assessment as compared to current standard practice, using an absolute 2.5% non-inferiority margin. Assuming a 28-day mortality of 15% in patients managed as suspected sepsis treated in the ED [3, 12], this means that any increase in 28-day mortality from 15% to not more than 17.5% would be considered non-inferior. For

90% power and one-sided 5% significance level the sample size required is 7002, assuming there is no difference in 28-day mortality between arms. Our patient focus group were also consulted on the 2.5% non-inferiority margin and felt that this was acceptable if there were mechanisms to monitor trial outcomes, and if this was what was needed to provide a sample size which would ensure the trial could be completed as well as answer the research question.

2. Initiation of antibiotics treatment, for which we want to show superiority. Currently around 90% of patients managed as suspected sepsis receive antibiotics (RLBUHT, unpublished data). A reduction by 10 percentage points to 80% would be considered a success. To detect such an effect with 90% power and two-sided 5% significance level the sample size required is 532, which is substantially lower than what is needed for the non-inferiority endpoint. With 7002 patients we would be able to detect effects as small as a reduction from 90% to 87.6% prescriptions, with 90% power.

Accounting for 5% dropout, we need a total sample size of 7372. We include one interim analysis (after 50% of patients have provided data) with options to stop the trial early using group-sequential O'Brien-Fleming boundaries [37, 38]. We will consider stopping for effectiveness if:

- the PCT guided assessment is superior in terms of 28-day mortality (i.e. a significant reduction to less than 15%), or
- the PCT guided assessment is non-inferior in terms of 28-day mortality and superior in terms of initiation of antibiotics.

We will consider stopping for futility if the results of the interim analysis suggest futility for both endpoints.

The group-sequential design will increase the total maximum sample size (if the study is not stopped after the interim analysis) by just over 4% to 7676 (inflated for 5% dropout). However, the sample size will be substantially smaller if the trial does get stopped early.

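### The 28-day mortality model adjusts only for NEWS2 and site; prespecifying age and reporting a standardised risk difference would give a modest gain in precision at almost no cost

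*Protocol*

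**What the plan says.** Section 17.1 (Main analysis) states that the primary analysis will "fit separate two-level logistic regression models (patients nested within sites) to both primary outcomes", "controlling for baseline NEWS2 score (minimisation factor"). No other covariate is named. Section 16.1 gives the design counterpart: "We will use minimisation with NEWS2 score and site as stratification factors". Model and minimisation therefore match, and neither involves age.

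Section 4 (Background) describes NEWS2 as an "assessment based on six vital signs and requirement for supplemental oxygen", so age is not part of the score as the protocol describes it. Section 8.1 admits patients from "16 years presenting to the ED with suspected sepsis", so age has to be checked at enrolment. Section 15.5.1 uses date of birth as an identifier on serious adverse event forms.

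Section 16.2 sizes the trial on mortality ("Assuming a 28-day mortality of 15% in patients managed as suspected sepsis treated in the ED"), with an absolute margin of 2.5 points, one-sided 5% significance, 90% power, no true difference, and 7002 patients before dropout and the interim allowance. Section 17.1 replaces that margin with an arcsine-difference frontier if control mortality departs from 15%.

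**The concern.** Mortality is the endpoint that drives the size of the trial: it needs 7002 patients, against 532 for antibiotic initiation. The population runs from 16 years upwards with no upper limit, and age can reasonably be expected to predict 28-day death beyond what vital signs carry. If it does, variation due to age stays in the residual variance of the mortality comparison, and chance imbalance in age passes into the estimate. Both can be reduced with a variable that is fixed before randomisation and needs no extra assessment. At stake is the width of the interval that is compared with the margin, and a little power. The validity of the analysis is not in question.

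**Working it through.** **1. The plan's own figure.** Inputs from section 16.2: mortality 15% in both arms, margin 2.5 points, one-sided 5%, 90% power. The standard formula without covariates gives 3495 per arm, 6990 in total, against the stated 7002 (0.2% apart). At 3501 per arm:

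- SE = √(2 × 0.15 × 0.85 / 3501) = 0.853 points
- Power = Φ(2.5/0.853 − 1.645) = 90.05%

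The planned power therefore does not depend on any adjustment.

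**2. What adjustment does to a standardised risk difference.** Its variance is multiplied by about (1 − R²), where R² = Var(predicted risk)/(0.15 × 0.85). Power becomes Φ(2.5/(0.853 × √(1 − R²)) − 1.645), and the further cut from adding age to NEWS2 is 1 − (1 − R²_both)/(1 − R²_NEWS2).

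**3. Assumptions, none of them given in the protocol.** Log-odds of death per SD of NEWS2 0.5 to 0.7; per SD of age 0.4 to 1.0; the two independent, taken as standard normal; intercept set so that overall mortality is 15%.

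**4. One scenario in full (NEWS2 0.5, age 0.8).** Averaging the logistic risk over both covariates gives R² = 0.0266 for NEWS2 alone and 0.1048 for both.

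- Variance cut: 1 − 0.8952/0.9734 = 8.0%
- NEWS2 only: SE = 0.853 × √0.9734 = 0.842; power = Φ(2.969 − 1.645) = 90.7%
- NEWS2 and age: SE = 0.853 × √0.8952 = 0.807; power = Φ(3.096 − 1.645) = 92.7%, a gain of 1.9 points before rounding

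**5. Whole range.**

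| Quantity | Age 0.4 to 1.0 | Age 0.6 to 0.8 |
|---|---|---|
| Further variance cut from age | 2.2 to 12.1% | 4.7 to 8.2% |
| Power gain, same scenario | 0.5 to 2.8 points | 1.1 to 1.9 points |

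Over the full range, power is 90.7 to 91.5% with NEWS2 only and 91.3 to 94.0% with age added. The precision gained equals about 150 to 960 extra patients under the NEWS2-only model, from 7002 × cut/(1 − cut).

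**6. A second set of assumptions.** With an age SD of 18 years and odds ratios of 1.2, 1.4, 1.6 and 1.8 per 10 years, the further cut is about 1, 4, 8 and 12%. Taking an added R² of 0.01 to 0.10 directly, on top of the unadjusted 90.05%, gives power of 90.3 to 92.6%, and the one-sided 95% half-width falls from 1.40 to between 1.40 and 1.33 points.

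**7. The odds-ratio scale.** Adding age to the logistic model raises the standard error of the conditional log odds ratio, by about 1 to 7% over the range in step 3 and 1 to 6% over that in step 6.

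**8. Chance imbalance.** With 3501 per arm, one standard error of the difference in mean age is √(2/3501) = 0.024 SD. Under step 3, risk rises by about 4.7 to 11.0 points per SD of age, so the unadjusted mortality difference shifts by 4.7 × 0.024 = 0.11 to 11.0 × 0.024 = 0.26 points, against a standard error of 0.85.

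**The case against.** The strongest reply is that nothing here is wrong. Both minimisation factors are in the model, the sample size assumed no adjustment, and type I error and power are intact. That stands in full. A reader might infer that leaving out age makes the trial underpowered or the mortality test invalid; section 16.2 does not support this, because its 7002 reproduces without covariates.

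A second reply is that the gain is not available in the model as written. This also stands. A reader might infer that simply adding age to the logistic regression sharpens the result; on the conditional odds-ratio scale it does the opposite (step 7). The benefit needs standardisation to a risk difference, and section 17.1 describes no such step.

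Third, the strength of age as a predictor, its distribution and its relation to NEWS2 are not in the protocol, so the size of the gain rests on assumptions. Completeness of age in the dataset is inferred from the eligibility threshold. The sentence "The participant will be identified only by trial number, date of birth and initials" concerns serious adverse event reports, which section 15 restricts to few events, and does not show that date of birth is held for everyone.

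Fourth, section 17.1 leaves full details to the SAP, which may add covariates. That is possible, but the protocol itself states the covariate for the primary models, so the point can be settled there whatever the SAP says.

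Finally, the imbalance argument is small. A one-standard-error imbalance moves the estimate by well under a third of its standard error, and the interval already allows for it. It is not a bias.

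**Conclusion.** The point holds as a missed efficiency. Under the stated assumptions, age cuts the variance of the mortality risk difference by a further 2 to 12% and adds about 0.5 to 2.8 points of power, with 1.1 to 1.9 points in the middle of the range. Subtracting the lowest NEWS2-only power from the highest age-adjusted power (94.0 − 90.7 = 3.3 points) would overstate the gain, because those ends belong to different scenarios. All of this depends on age predicting death beyond NEWS2, on age being recorded for essentially everyone, and on the result being reported as a standardised risk difference. If age were correlated with NEWS2, the gain would probably differ from these figures, which assume independence. Confidence is moderate: the omission is plain in the text, while its size is assumed.

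**What to change.** In section 17.1, specify that the mortality model includes baseline NEWS2, age (continuous, with a spline or quadratic term to allow non-linearity) and site. State that the mortality difference and its confidence limit are obtained by averaging the model's predicted risks under each arm over all patients analysed, giving a marginal risk difference on the scale of the 2.5-point margin. The two standardised risks can also feed the arcsine frontier if that replaces the margin. Keep the NEWS2-only model as a sensitivity analysis. Adding age to the antibiotic-initiation model is optional, since that endpoint has ample power.

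The cost is a sentence or two of protocol and SAP wording and a check that age is complete in the trial database; no new patients or assessments are needed. Because the trial is open label, the change should be fixed and dated before those choosing the model have seen any comparison of outcomes by arm, interim results included.

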5.3 Primary outcomes measure(s)

The study will use the following as co-primary outcomes:

- Intravenous antimicrobial initiation – binary outcome assessed at 3 hours.
- 28-day mortality – binary outcome.

Final decisions about the primary effectiveness, using these co-primary outcomes will be made based on:

	Reduced antibiotic initiation	Same or more antibiotic initiation
Decreased mortality	Effective	Effective
Equivalent mortality	Effective	Not effective
Increased mortality	Not effective / harmful	Not effective / harmful

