This will be used in combination with NEWS2 assessment of adult patients with suspected sepsis in ED, using a guidance-only algorithm for clinicians (see flow chart). It is important to note that clinicians have oversight at all times as to whether to adhere to the algorithm. As currently mandated in NICE clinical guidelines and quality standard QS161, urgent senior review within an hour will take place where any health care provider identifies at least one risk factor indicating high risk of severe illness or death regardless of aetiology. In the intervention arm a NEWS2 score of 5 or 6, combined with a PCT score of <0.5 indicates a low risk of bacterial sepsis, but an urgent senior review is mandated on the basis of the elevated NEWS2 score in keeping with standard QS161. For participants who are identified as medium risk, urgent senior review will occur. Antibiotics will be delivered according to clinical assessment. For participants in the high risk categories (Figure 1, red boxes), antibiotics will be given within the hour along with blood tests and IV fluids given as per standard care.

The PCT result is a decision aid and not to be used as a definitive management decision tool. Trained HCPs will perform the test in the ED, without the need to send the PCT sample to the laboratory. A rapid result, especially if it indicates a low or medium risk, may provide reassurance to patients and families, and reduce anxiety.

[figure not shown]
Full administrator level training will be provided by Thermofisher or AB Scientific at each site with all users following the appropriate Standard Operating Procedure for QC measurement and routine work flow processes (see example of BRAHMS PCT Direct in Figure 3). For the BRAHMS PCT Direct, Research Nurses or appropriately delegated HCPs will have a unique 4-

digit log in code for the reader. Adults in the control arm will not have the PCT test performed and will simply have NEWS2 assessment for suspected sepsis as per standard care.

Thermo Scientific B·R·A·H·M·S direct Reader

Routine workflow

1/3

thermo scientific

Figure 3. Routine work flow for BRAHMS PCT-Direct Reader.

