10.1 Adherence

Adherence to the algorithm will be recorded on the CRF and will capture instances where the treating clinician overrules the algorithm if they feel it is appropriate to do so. The ultimate responsibility for clinical care of the patient lies with the treating clinician therefore the cut – off boundaries for initiation times of antibiotics are not mandatory but are recommended guidance to aid clinical decision making. The aim of the trial is to assess whether the use of PCT can improve decision making about which patients receive antibiotics and in what time period. Deviations from the algorithm will not be recorded as protocol violations.

11 Trial procedures

All participants will be prospectively enrolled in the trial from the date of randomisation and will be assessed up to and including day 28 or until they are discharged from clinical care (for those enrolled in the last three months of the trial). Assessments include antibiotic initiation, antibiotic use, adverse events, ICU usage (details of admission to ICU), unscheduled readmissions (ICU re-admissions, re-admissions post discharge), mortality (death for any reason in the 28 days following randomisation), discharge before Day 28, and serious adverse drug reactions (ADRs) to the antibiotic. All clinical management decisions will be recorded at all time points.

At Day 28 and Day 90 there will be a follow-up via telephone or electronically (email/text) about the healthcare utilisation and quality of life of the participant. If unsuccessful a questionnaire booklet will be posted to the participant for them to complete and return with a pre-paid envelope.

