Number of sites open	>7 5-7 <5	GO Discuss potential mitigating strategies REVIEW/STOP
Number of enrolled participants	>2000 1000-2000 <1000	GO Discuss potential mitigating strategies REVIEW/STOP
Eligible patients randomised (defined as number randomised/number screened and on screening log*)	>50% 30-50% <30%	GO Discuss potential mitigating strategies REVIEW/STOP
Consent rate (defined as number with informed consent from patient or consultee agreement/number randomised)	>85% 50-85% <50%	GO Discuss potential mitigating strategies REVIEW/STOP
Consideration of the PCT result and algorithm during clinical decision making (defined as number algorithm adhered too /number PCT result recorded)	>50% 35-50% <35%	GO Discuss potential mitigating strategies REVIEW/STOP
Ability to collect co-primary outcome data (defined as number with complete data for both co-primary outcomes/number randomised)	>90% 70-90% <70%	GO Discuss potential mitigating strategies REVIEW/STOP
Ability to collect 28- and 90-day follow up data (defined as number with complete follow up data/number randomised)	>70% 50-70% <50%	GO Discuss potential mitigating strategies REVIEW/STOP
Reduction in the % of patients treated within time windows for usual standard care (defined as Prospective usual Standard care treatment window data/Retrospective treatment window)	<10% 10-20% >20%	GO Amend processes REVIEW/STOP
Contamination/changes to usual care in control arm	Qualitative interviews	

- Screening log will only be active during periods when a research nurse is time tabled to be in the ED/admissions unit

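### The second complier definition (algorithm followed exactly) treats patients whose PCT result was used but not exactly followed as unaffected, so its causal estimate is biased in a direction the protocol cannot fix

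*Protocol*

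**What the plan says.** Protocol section 17.1 sets the primary analysis as intention to treat: "The primary analysis will be intention to treat and will fit separate two-level logistic regression models". It then adds: "In a secondary analysis, complier adjusted causal effect models will be fitted to allow for non-adherence to the intervention". Two definitions of adherence are fixed there, and both require a PCT test in a patient randomised to PCT-guided care. Under definition 1, "the clinician considers the results as part of their decision making". Under definition 2, "the clinician follows the algorithm exactly". The estimator is not named, and the section leaves full details to the SAP, which was not available for this review.

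Section 10 presents the algorithm as guidance only and the PCT result as a decision aid. Control patients are not tested. For the high-risk categories, "antibiotics will be given within the hour along with blood tests and IV fluids given as per standard care"; for medium risk, antibiotics are left to clinical assessment. Section 10.1 says that the algorithm's cut-offs concern antibiotic initiation times and are not mandatory, and that the CRF "will capture instances where the treating clinician overrules the algorithm". The antibiotic co-primary outcome in section 5.3 is IV initiation, a "binary outcome assessed at 3 hours".

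**The concern.** A complier effect that uses randomisation as the instrument rests on the exclusion restriction: assignment must not change the outcome of anyone classed as a non-complier. Definition 2 puts into that class every tested patient whose clinician saw the result, weighed it and then departed from the algorithm in some respect. By the protocol's own description, the result may have changed what was done for such a patient.

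The definition also overlaps with the outcome. If the algorithm is about when antibiotics start, whether it was followed is decided partly by whether and when they started. For medium-risk patients, where the decision is left to clinical assessment, it is unclear what exact adherence means.

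At stake is a secondary estimate that readers could take as the effect to expect when the algorithm is fully followed. It would mix the effect in exact followers with an effect borrowed from everyone else.

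**Working it through.** The protocol gives no figure for the complier analysis, so there is none to reproduce. The 10-point effect used below is the antibiotic target in section 16.2 (90% to 80%), borrowed as an illustrative effect in exact followers. The 532 patients stated there for that target (90% power, two-sided 5%) do reproduce.

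**Step 1. The two definitions against each other.** Take definition 2 as a subset of definition 1, which is how it should work in practice. This leaves a middle group: tested, result considered, not exactly followed. Definition 1 treats the group as exposed; definition 2 requires it to be unaffected. Both models can be valid only if the effect in this group is zero.

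**Step 2. Formula.** Control patients are not tested, so non-adherence is one-sided. On the risk-difference scale:

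- p1 = share meeting definition 1, and p2 = share meeting definition 2, among all randomised to PCT
- E = true effect in exact followers
- s × E = effect in the middle group
- patients outside definition 1 are taken as unaffected
- ITT = p2 × E + (p1 − p2) × s × E
- Definition 2 estimate = ITT / p2 = E × [1 + s × (p1 − p2) / p2]

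**Step 3. Numbers.** All inputs are assumptions: p1 = 0.90, p2 = 0.50, E = 10 points. Then ITT = 5 + 4s, and the estimate is (5 + 4s) / 0.5.

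| s | ITT | Definition 2 estimate | True E | Ratio |
|---|---|---|---|---|
| −0.5 | 3.0 | 6.0 | 10 | 0.6 |
| 0 | 5.0 | 10.0 | 10 | 1.0 |
| 0.25 | 6.0 | 12.0 | 10 | 1.2 |
| 0.5 | 7.0 | 14.0 | 10 | 1.4 |
| 1 | 9.0 | 18.0 | 10 | 1.8 |

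With p2 = 0.35, the estimate is (3.5 + 5.5s) / 0.35. It runs from 2.1 points at s = −0.5, through 10 at s = 0, to 25.7 at s = 1.

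**Step 4. Overlap with the outcome.** These strata are invented for illustration. The low-risk rows assume that adherence means no IV antibiotics, because Figure 1 is not available to confirm it.

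- *High risk, adherent means antibiotics given.* 85% treated under either arm, 10% only under control, 5% under neither. ITT = −10 points and adherent share = 0.85. The true effect in adherers is 0, since all of them would be treated either way. Estimate = −10 / 0.85 = −11.8.
- *Low risk, adherent means no antibiotics.* 60% treated under either arm, 20% only under control, 20% under neither. ITT = −20, adherent share = 0.40, true effect = −20 / 0.40 = −50, estimate = −50. No bias.
- *Low risk, with PCT prompting antibiotics in 5%.* 55%, 20%, 5% (only under PCT) and 20%. ITT = −15, adherent share = 0.40, true effect = −50, estimate = −15 / 0.40 = −37.5. Understated.

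The sign of the bias therefore depends on the risk mix and on why clinicians depart from the algorithm. The protocol gives neither.

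**The case against.** The strongest case on the other side is that the analysis is secondary, the effectiveness decision rests on intention to treat, definition 1 is fitted alongside, and the estimator, covariates and sensitivity analyses belong in the SAP. All of that is true, and it limits the consequence. It does not rescue definition 2. The definition is fixed in the protocol, and any estimator that relies on randomisation as its instrument inherits the problem. An estimator that avoids it must lean on covariate assumptions instead, and is then no longer protected by randomisation. Fitting definition 1 as well does not make the second model valid.

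A reader might infer several stronger points that the documents do not support.

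- *That definition 2 necessarily overstates the effect.* This needs the middle group to be shifted the same way as exact followers. That is plausible, but the bias is zero if they are unaffected and reversed if they are shifted the opposite way.
- *That the scaling itself is the error.* Dividing by 0.5 is what any complier analysis does at 50% compliance, and it is right if non-compliers are unaffected.
- *That the pilot threshold gives the complier share.* Section 13, Table 2 uses "number algorithm adhered too /number PCT result recorded". It does not say exact, and its denominator leaves out patients randomised to PCT who have no recorded result.
- *That adherence is judged mainly from the outcome.* The visible text supports only partial overlap: the high-risk target is one hour while the outcome is at three hours, and medium risk is left to judgement.
- *That the mortality comparison is distorted.* A zero difference stays zero after division, and the estimate and its standard error scale together. The interval widens, which is lost precision and not bias. The protocol does not apply the 2.5-point margin to this analysis.
- *That the result would be presented as protected by randomisation.* Section 17.1 says only that the models allow for non-adherence.

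**Conclusion.** The concern holds in this form: the exclusion restriction is not credible for definition 2, because the protocol itself describes a route by which PCT can affect patients whom that definition calls non-compliers, and because adherence overlaps with the antibiotic outcome. The two planned models agree in their assumptions only if patients with a considered but not exactly followed result have no effect.

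Under the assumptions in the working (90% meeting definition 1, 50% meeting definition 2, a true 10-point effect), the estimate ranges from 6 to 18 points as the effect in that group goes from −50% to 100% of the effect in exact followers. It is correct at zero. These figures show sensitivity; they do not predict the bias. Adherence shares, risk mix and the content of Figure 1 are all needed to fix direction and size, and none is available. The primary intention-to-treat conclusion is unaffected. The point is worth correcting because a secondary causal estimate is specified on an assumption that the protocol contradicts.

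**What to change.** In section 17.1, define compliance for the causal model by exposure to the PCT result: test done, and result available to or considered by the clinician before the antibiotic decision. Remove definition 2 from that model, and report exact algorithm adherence descriptively by risk category, using the CRF data already planned in section 10.1.

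If an effect of exact adherence is still wanted, label it exploratory, state that it is not protected by randomisation, and add a sensitivity analysis over the effect in patients whose result was considered but not exactly followed. The table in the working shows one way to lay that out.

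The cost is protocol and SAP wording. No new data are needed, and one secondary causal estimate is dropped or relabelled.
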